15.2 Placebo

15.2.1 **Formulation:** Matched placebo capsules are provided in identical PEA-Placebo labeled bottles for dispensing. Each placebo capsule contains 400mg dextrose in a size 0 transparent Hydroxypropyl methylcellulose (HPMC) capsule.

15.2.2 **Storage:** Products are to be stored in the original container below 25°C. Containers should be stored tightly closed.

16.0 Statistical Considerations

16.1 Statistical Design

This trial is designed as a randomized placebo-controlled pilot trial with the primary objective of estimating the efficacy of two dose levels of PEA to inform the design of a future phase III trial for treatment of chemotherapy-induced peripheral neuropathy (CIPN). Patients will be randomized 2:2:1:1 to receive either 400 mg of PEA (one 400 mg capsule), 800 mg PEA (two 400 mg capsules), 1 placebo capsule, or 2 placebo capsules, respectively. The two placebo arms are included in this study to ensure that there is a matched number of capsules for each of the PEA arms; however, all placebo patients will be analyzed as one group (a combined placebo arm). The efficacy of the two dose levels of PEA will be estimated as the difference between each dose level of PEA compared to the combined placebo arm.

16.2 Sample size, Accrual time and Study Duration

16.2.1 Sample size

As this is a pilot trial to estimate the efficacy of PEA, the sample size is based on feasibility considerations and estimation precision. We plan to accrue a total of 88 patients (consisting of 78 evaluable patients + 10% dropout due to cancellation or ineligibility). Based on our previous trial experience [98], by assuming the standard deviation of the 0-100 scale transformed CIPN20 change score is 15 in each treatment arm. With this assumption, 26 patients per PEA arm and 26 total patients for the combined placebo arm (pooling all patients receiving

placebo together for statistical analysis) allows estimation of the difference between two arms, of the CIPN20 score change from baseline to 8 weeks, with a 95% two-sided confidence interval width of 16.8 points.

16.2.2 Accrual time and study duration

We assume that the accrual rate will be about 6 patients per month; if true, the anticipated study period for accruing 88 patients will be 15 months. With data from the primary endpoint maturing 8 weeks later, the primary analysis can begin approximately 17 months after the trial begins; as soon as all patients have completed 8 weeks of treatment and submitted QOL booklets or have gone off protocol treatment.

16.3 Primary Endpoint Analysis Plan

16.3.1 Primary endpoint analysis

The primary endpoint is the CIPN20 score ([Appendix II](#)). The CIPN20 questionnaire will be scored and summarized at each time point for each patient (see Section 11.1). The change from baseline to 8 weeks will then be calculated for each patient. The mean (standard deviation) and median (range) of the change will be calculated for each PEA arm and the combined placebo arm. The difference in change scores between each PEA arm and the combined placebo will be estimated along with a 95% confidence interval. For the primary analysis, the CIPN20 analysis dataset will include all eligible patients who are randomized, initiated treatment, and completed the baseline questionnaire. For patients who go off protocol treatment before 8 weeks, the score at their final observation will be used to calculate the change. For patients who do not have any post baseline data, they will be considered to have no change from baseline. Sensitivity analysis based on imputation of missing data as described in Section 16.5 will be performed using similar methods.

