3.1 Registration -- Inclusion Criteria

- 3.1.1 Age \geq 18 years.
- 3.1.2 ECOG Performance Status 0, 1, 2 (Form available on ACCRU website).
NOTE: Patients with a history of metastatic cancer or an ECOG Performance Status of 2 must have lab work (see Section 3.1.9) completed \leq 28 days prior to registration.
- 3.1.3 Pain, numbness, tingling or other symptoms of CIPN of \geq 3 months (90 days) duration for which the patient is seeking an intervention.
- 3.1.4 Neurotoxic chemotherapy must have been completed \geq 3 months (90 days) prior to registration and there must be no further planned neurotoxic chemotherapy for $>$ 2 months after registration.
Note: The study is limited to those with taxane- and/or platinum-based neuropathy.
- 3.1.5 Patient must note tingling, numbness or pain symptoms of at least a four out of ten \leq 7 days prior to registration.
Note: On a 0-10 scale where zero was 'no problem' and ten being 'as bad a problem that could be imagined': *how much of a problem has numbness, tingling,*

and/or pain in your fingers and/or toes been in the past week? (patient verbal report utilizing question 1 in [Appendix VI “Peripheral Neuropathy Questions”](#)).

- 3.1.6 Patient must be able to speak, read and comprehend English.
- 3.1.7 For women of childbearing potential only, a negative urine or serum pregnancy test done \leq 14 days prior to registration is required.
A female of childbearing potential is a sexually mature female who: 1) has not undergone a hysterectomy or bilateral oophorectomy; or 2) has not been naturally postmenopausal for at least 12 consecutive months (i.e., has had menses at any time in the preceding 12 consecutive months).

NOTE: If the urine test cannot be confirmed as negative, a serum pregnancy test will be required.

- 3.1.8 Life expectancy \geq 6 months.
- 3.1.9 Required Initial Laboratory Values: Following completion of chemotherapy, patients must have had a CBC and serum chemistries, including the following:
 - Platelet count $> 100,000/\text{mm}^3$
 - Absolute neutrophil count (ANC) $\geq 1,000/\text{mm}^3$
 - Hemoglobin $> 11 \text{ g/dL}$
 - Serum transaminase [ALT or AST] $\leq 1.2 \times$ upper limit of normal (ULN)
 - Alkaline phosphatase $\leq 1.2 \times$ ULN
 - Serum creatinine $\leq 1.2 \times$ ULN

NOTE: Patients with a history of metastatic cancer or an ECOG Performance Status of 2 must have these labs completed \leq 28 days prior to registration.

- 3.1.10 Able to swallow oral medication.

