4.1 Survival Follow-up

After completing 8 weeks of treatment, patients will proceed to survival follow-up. A Nurse/Research Coordinator will contact the patient to inquire about neuropathy status, disease status, and survival at both 6 months (\pm 30 days) and 12 months (\pm 30 days) after registration. There will be no additional follow-up after these two timepoints. ([Appendix IX](#))

5.0 Stratification Factors:

- Gender: Male vs Female
- Prior Chemotherapy Received: Any **Taxane** ± **carboplatin** ± other agents versus **Oxaliplatin** based versus **other** (never received a taxane nor oxaliplatin)

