6.3 Randomization Procedures

6.3.1 The factors defined in Section 5.0 will be used as stratification factors.

6.3.2 After the patient has been registered into the study, the values of the stratification factors will be recorded, and the patient will be assigned to one of the following treatment groups using the Pocock and Simon dynamic allocation procedure which balances the marginal distributions of the stratification factors between the treatment groups [105].

- Palmitoylethanolamide: 400 mg (1 capsule daily) PO for 8 weeks
- Palmitoylethanolamide: 800 mg (1 400mg capsule twice daily) PO for 8 weeks

- Placebo: 1 capsule PO daily for 8 weeks
- Placebo: 1 capsule PO twice daily for 8 weeks

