16.4.2 Exploratory endpoint analysis

16.4.2.1 The two cognitive items of the Cognitive Functioning Assessment ([Appendix VII](#)) will be summarized by mean (SD) and median (range) at each time point for each PEA arm and the combined placebo arm. The mean change from baseline to 8 weeks will be estimated along with the 95% confidence interval for each PEA arm and the combined placebo arm.

16.4.2.2 The weekly CIPN20 scores will be summarized at each time point by mean (SD) and median (range) and will be plotted longitudinally for each PEA arm and the combined placebo arm.

16.4.2.3 The weekly pain scores ([Appendix VI](#)) will be summarized at each time point by mean (SD) and median (range) and will be plotted longitudinally for each PEA arm and the combined placebo arm.

16.4.2.4 Items of the Global Impression of Change tool ([Appendix III](#)) will be summarized by frequency (percentage) of each level at each time point for each PEA arm and the combined placebo arm. Bar plots for each PEA arm and the combined placebo arm of frequency over time will be constructed.

16.4.2.5 The Chemotherapy Induced Peripheral Neuropathy Assessment Tool ([Appendix IV](#)) will be summarized by mean (SD) and median (range) at each time point for each PEA arm and the combined placebo arm.

16.4.2.6 Using the changes scores constructed for the primary endpoint, the difference in CIPN20 change scores between the two PEA dosage arms will be estimated along with a 95% confidence interval.

16.4.2.7 Evidence of disease recurrence and the date of recurrence will be asked by nurse at the 6 and 12 months' follow-up ([Appendix IX](#)). The number of events and percentage will be reported by each PEA arm and combined placebo arm. No hypothesis test will be performed between arms.

16.4.2.8 Overall survival is defined as the time from registration to death due to any cause. For each PEA arm and combined placebo arm, the distributions of OS time will be estimated using the Kaplan-Meier method. Log-rank test will be used to compare the survival distributions between each PEA and the combined placebo arm.

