16.5 Missing Data

We will examine the mechanisms of missing data if the proportion of missing assessments for the primary endpoint is not small ($\geq 10\%$). Graphical presentation, correlation analysis (Kendall's) and logistic regression will be performed to examine whether the missing data mechanism depends on the covariates (patient characteristics

and other baseline risk factors), observed patient-reported outcome (PRO) scores, and missing PRO scores.

If the missingness is completely at random (MCAR), complete case analysis will be conducted.

If the missingness depends on covariates and observed PRO scores (missing at random, MAR) [99] [100], the data will be analyzed using the (generalized) linear mixed models with patient as the random effect and treatment along with all factors associated with data missingness will be included as predictors in the models. [100].

If there are indications that the missingness is not at random (MNAR),, we will explore advanced models that consider both longitudinal PRO assessments and missing data mechanism, such as pattern mixture model and selection model[100].

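### The primary CIPN20 comparison is an unadjusted difference in change scores; pre-specified adjustment for baseline CIPN20 and the two randomisation factors would usually narrow the interval at almost no cost.

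*Combined protocol and SAP*

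**What the plan says.** Section 16.3.1 computes each patient's CIPN20 change from baseline to week 8 and then describes it by arm: "The mean (standard deviation) and median (range) of the change will be calculated for each PEA arm and the combined placebo arm". The comparison follows: "The difference in change scores between each PEA arm and the combined placebo will be estimated along with a 95% confidence interval". The exploratory dose contrast in 16.4.2.6 uses the same scores: "the difference in CIPN20 change scores between the two PEA dosage arms will be estimated along with a 95% confidence interval". None of these sentences mentions a model or a covariate.

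The precision statement in 16.2.1 assumes that the "standard deviation of the 0-100 scale transformed CIPN20 change score is 15 in each treatment arm", with 26 evaluable patients in each PEA arm and 26 on pooled placebo, and gives a 95% interval width of 16.8 points.

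Section 5.0 lists two stratification factors, gender (two levels) and prior chemotherapy (three levels). Section 6.3.1 puts them into a Pocock-Simon allocation: "The factors defined in Section 5.0 will be used as stratification factors". Neither factor is named in Section 16.

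Covariate modelling appears only in Section 16.5. If at least 10% of primary assessments are missing and the missingness looks MAR, a mixed model is fitted in which "treatment along with all factors associated with data missingness will be included as predictors in the models".

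**The concern.** Subtracting baseline fixes the slope of week-8 score on baseline at 1. A linear model with baseline as a covariate estimates that slope, and its residual variance is no larger whatever the true slope. The two are equal only when rho x SD8/SD0 = 1, where rho is the correlation between baseline and week 8, and SD0 and SD8 are the SDs at those times. The two randomisation factors are balanced by design and then left out of the analysis.

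Precision is what this trial is built to deliver. Its aim (Sections 2.1 and 16.1) is to estimate two PEA-placebo differences for a phase III design, and 16.2.1 justifies the sample size by feasibility and by the width of this interval, with 26 patients per group. Section 16.3.1 admits only patients who completed the baseline questionnaire, so adjusting for baseline loses no patient and needs no new data. Section 16.5 does not fill the gap: it is a conditional sensitivity analysis, and it chooses covariates for their link to missingness.

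**Working it through.** **Inputs.** From 16.2.1: SD of change 15, 26 per group, two-sided 95%. From 16.1: 2:2:1:1 allocation, which is 1:1:1 once placebo is pooled. Assumed, because the documents do not give them: rho and k = SD8/SD0.

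**1. The plan's own figure.** SE = 15 x sqrt(2/26) = 4.160. Width = 2 x t(0.975, 50) x 4.160 = 16.71. The stated 16.8 is 0.5% higher, so it matches an unadjusted two-sample interval. With an SD pooled over three groups (75 df) the width is 16.58.

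**2. Adjusting for baseline.** Variance of change = SD0² + SD8² - 2 rho SD0 SD8. Residual variance after regression on baseline = SD8²(1 - rho²). The ratio of the second to the first is

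R = k²(1 - rho²) / (1 + k² - 2 rho k), which is (1 + rho)/2 when k = 1.

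The pairwise adjusted width is 2 x t(0.975, 49) x 4.160 x sqrt(R). Chance baseline imbalance adds a factor of about 1 + 1/48 to the variance, or 1% to the width. Widths, with that loss included in brackets, against 16.71 unadjusted:

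| k | rho 0.5 | rho 0.7 | rho 0.8 | rho 0.9 |
|---|---|---|---|---|
| 0.8 | 12.64 (12.77) | 13.25 (13.38) | 13.38 (13.52) | 13.04 (13.17) |
| 1.0 | 14.48 (14.63) | 15.42 (15.58) | 15.86 (16.03) | 16.30 (16.47) |
| 1.2 | 15.60 (15.77) | 16.44 (16.61) | 16.69 (16.87) | 16.53 (16.70) |

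At k = 1.25 and rho = 0.8, R = 1.000 and the width is 16.72 (16.89), so there is no gain.

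At k = 1, before the loss, the savings are 2.2, 1.3, 0.8 and 0.4 points. The equivalent unadjusted group size is 26/R = 34.7, 30.6, 28.9 and 27.4.

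**3. One three-group model with all covariates.** Baseline takes 1 df, gender 1 and prior chemotherapy 2, leaving 75 - 4 = 71. At k = 1, with the same 1/48 allowance, the widths are 14.52, 15.45, 15.90 and 16.34, against 16.58 unadjusted on this basis.

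**4. What the two factors add.** This was simulated with 1,500 runs per setting, 78 patients in three groups, minimisation with an assumed 0.9 probability, 43% men (38 of 88 in Section 16.8), an assumed 60/35/5 chemotherapy split, and k = 1. Mean width with baseline only, then with baseline plus both factors:

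| rho | factors not prognostic | gender explains an assumed 5% of residual variance |
|---|---|---|
| 0.5 | 14.39, 14.44 | 14.47, 14.13 |
| 0.7 | 15.37, 15.41 | 15.32, 14.97 |
| 0.9 | 16.21, 16.28 | 16.22, 15.87 |

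The factors cost 0.04 to 0.07 points if they are not prognostic and save about 0.35 in the assumed prognostic case.

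**5. Worst case.** In a separate simulation (minimisation probability 0.8), baseline and both factors were unrelated to change. The mean pairwise width rises from 16.67 to 16.95 (+0.28). The three-group model gives 16.76, which is 0.09 above the pairwise unadjusted mean and 0.18 above the 16.58 in step 1. Coverage stays near 95%.

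**The case against.** The plan contains no error. The endpoint, the SD and the stated width all refer to change, they agree with one another, and the estimator is unbiased. No decision threshold is attached to the interval, so no phase III choice visibly turns on a narrowing of 0.4 to 2.2 points. The gain depends on two quantities that the documents do not supply. At k = 1.2 with the imbalance loss counted, three of the four correlations save 0.1 points or less, and rho = 0.8 gives a slight widening. A k above 1 is conceivable, because entry requires a symptom score of at least 4 out of 10, which may compress baseline spread, although on a different scale from CIPN20. The factors have no general argument behind them, only a conditional one. The threshold in any rule for pooling chemotherapy levels is a matter of judgement. That the analysis is unadjusted is itself inferred from silence.

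Most of these facts stand, and they set the strength of the recommendation. They do not overturn it. The inference is firm: there is no model, the summaries are raw, and the planned width is that of a two-sample interval. In an estimation trial the interval is the product, and the possible gain (up to about 4 points on the grid above) is far larger than the possible loss (0.1 to 0.3 points).

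**Conclusion.** The point holds as a recommended improvement in efficiency, not as a correction of bias. Adjusting for baseline CIPN20 narrows the planned interval over most of the range examined: by 2.2 to 0.4 points for rho from 0.5 to 0.9 if the SDs are equal, by about 3.3 to 4.1 if the week-8 SD is 0.8 of the baseline SD, and by 1.1 to almost nothing if it is 1.2 times the baseline SD. These savings are before the 1% loss for chance imbalance. They rest on assumed correlations and SD ratios and on the plan's SD of 15. The case for including gender and prior chemotherapy is weaker, since the documents do not say that either is prognostic, but the price is a few hundredths of a point. Adjustment does not address the handling of early discontinuation and missing follow-up in 16.3.1.

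**What to change.** In 16.3.1, name as the primary estimate, with its 95% interval, a linear model of CIPN20 change on treatment (three groups), baseline CIPN20, gender and prior-chemotherapy type. Fit it once to all three groups, and take the 16.4.2.6 dose contrast from the same model. Keep the unadjusted differences and the arm summaries as supportive output.

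State a rule in advance for the third chemotherapy level, defined in Section 5.0 as "never received a taxane nor oxaliplatin". Eligibility criterion 3.1.4 says "The study is limited to those with taxane- and/or platinum-based neuropathy", so this level should hold only platinum patients who had neither oxaliplatin nor a taxane, and it may be very small. At the 5% assumed above it would be 0.05 x 78 = 3.9 patients, or 1.3 per group. One workable rule, applied to blinded counts, merges it with the oxaliplatin level if it averages fewer than 3 patients per analysis group. The threshold and the merge partner are judgements for the team to settle before unblinding.

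The cost is SAP wording. Every covariate is already collected, and the model uses 4 of 75 residual degrees of freedom, or 3 if the levels are merged. The model should be fixed before unblinding, so that covariates cannot be chosen on the results.

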Three publications are particularly illustrative of the safety and efficacy of PEA in treating pain. A post hoc analysis of a multi-center double-blind, placebo-controlled, 3-armed trial involved patients with lumbosacral pain; the two treatment arms were micronized PEA, 300 and 600mg daily and the third was placebo.[81] The duration of treatment was 21 days. The outcomes were the change in the visual analog scale (VAS) (0 no pain 10 severe pain) and the Roland-Morris Disability Questionnaire (RMDQ). The number needed to treat to benefit a single individual (NNT) was calculated using the response criteria of a 50% improvement in pain relief and a 50% improvement in the RMDQ. Attrition due to side effects was determined and the number needed to harm due to discontinuation for reasons of adverse effects was the safety outcome. The study registered 626 patients of which 619 were evaluable. Both treatment arms were superior to placebo ($P<0.001$). Efficacy was particularly superior in the subgroup with neuropathic pain. For the 300 mg arm, the NNT for pain relief was 9 (95% confidence intervals 5-29) and the RMDQ NNT was 6.4 (95% confidence interval 4-14) ($P<0.02$). For the 600 mg treatment arm the NNT for pain relief was 1.7 (95% confidence intervals 1.4 - 2) and the RMDQ NNT was 1.5 (1.4 - 1.7) ($P<0.001$). The NNH was not different between treatment arms. Dropouts were 19 from placebo treatment, 2 from the 300mg treatment arm and 1 from the 600mg treatment arm.[81]

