7.2 Submission of Patient Completed Measures (Booklets)

Patient-completed questionnaire booklets for this study are to be ordered prior to the registration of any patients. The booklet order form is located on the ACCRU website under 'Manuals and Forms. Samples of questionnaire booklets are available in Appendices II-VII for reference and IRB submission only. Booklets must be given to patients to complete and patients should be instructed to return the booklets to site staff either in person or by mail and site staff will enter patient responses into Medidata Rave. At visits in which booklets are to be completed, the booklet should be given to and completed by the patient before any discussion of the patient's health status or test results. The PRO submission schedule is provided in the Study Calendar.

Baseline Booklet: The baseline questionnaire booklet should be completed in clinic on the same day as registration and returned to study staff. In the event the patient is unable to complete while in the clinic, the patient may complete at home and return by mail prior to starting the study medication.

Weekly Booklets: Questionnaire booklet(s) will be provided to patients to complete at home on a weekly basis for a total of eight weeks. Before the booklets are given to the patients, the nurse/study assistant will label each booklet with the week number and the anticipated 7-day weekly cycle start dates, in chronological order. Patients should be instructed to return the booklets by mail weekly. If, by chance, the patient has a regularly scheduled clinic visit at any time during the study period, the patient could return that

week's questionnaire during the clinic visit. Institutions must provide patients with sufficient self-addressed stamped envelopes for this purpose. Site staff will enter patient responses into Rave upon receipt of the completed booklets.

Verbal administration of the measures for visually impaired patients is permitted if the measure and verbal administration of the measure is conducted in a language understandable to the patients.

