13.0 Treatment/Follow-up Decision at Evaluation of Patient

13.1 Treatment Duration/Off protocol treatment

Protocol treatment is to continue for eight weeks. If patient discontinues treatment for any reason prior to the end of the eight weeks, they will proceed to Survival Follow-up per Section 4.1 until 1 year post-registration. All attempts should be made to collect patient questionnaires until the last date the patient received any protocol treatment.

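### The primary 8-week change pools week-8 scores, last on-treatment scores and assumed zeros under one label, has no rule for an unreturned week-8 booklet, and relies on a sensitivity plan in 16.5 that cannot work as written

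*Combined protocol and SAP*

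**What the plan says.** Sections 16.2.1 and 16.3.1 define the quantity as the CIPN20 change from baseline to 8 weeks, compared between each PEA arm and pooled placebo with a 95% interval. Section 16.3.1 gives two handling rules:

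- Early stoppers: "For patients who go off protocol treatment before 8 weeks, the score at their final observation will be used to calculate the change".
- No later data: "For patients who do not have any post baseline data, they will be considered to have no change from baseline".

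Section 13.1 limits collection after stopping: "All attempts should be made to collect patient questionnaires until the last date the patient received any protocol treatment". An early stopper's last score is therefore normally an on-treatment score. Section 7.2 has the weekly booklets completed at home: "Patients should be instructed to return the booklets by mail weekly".

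For robustness, 16.3.1 says: "Sensitivity analysis based on imputation of missing data as described in Section 16.5 will be performed using similar methods". Section 16.5 examines the missing-data mechanism "if the proportion of missing assessments for the primary endpoint is not small", defined as 10% or more. It tests dependence on covariates and on "observed patient-reported outcome (PRO) scores, and missing PRO scores". It then assigns complete-case analysis, (generalized) linear mixed models, or pattern-mixture and selection models according to the mechanism diagnosed.

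Section 16.4.1.2 repeats both handling rules for quality of life, and 16.4.2.6 reuses the primary change scores to compare the two doses.

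**The concern.** The pilot exists to supply an estimate for designing a phase III trial (sections 2.1 and 16.1), so a reader must know which effect the estimate describes. Three things get in the way.

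1. One mean, SD and interval combine true week-8 changes, last on-treatment changes and zeros that were never observed. The first two could together be read as a last on-treatment summary, but the plan does not say so, and an assumed zero does not fit that reading.
2. A patient who finishes treatment and returned some booklets, but not week 8, is in the analysis set and meets neither rule. Whether to exclude that patient or carry a score forward would be decided after the data exist.
3. The sensitivity analysis points to an imputation procedure that 16.5 does not contain. What 16.5 does contain depends on telling missing at random from missing not at random. Observed data cannot do that, because the deciding scores are the missing ones.

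**Working it through.** **Inputs from the documents.** SD of change 15, 26 per compared group, 78 evaluable (16.2.1). Dropout in the 2017 meta-analysis in 1.7.4: 1.1% on PEA and 4.3% on control. Low-back-pain trial in 1.7.4: "Dropouts were 19 from placebo treatment, 2 from the 300mg treatment arm and 1 from the 600mg treatment arm", 626 patients registered, 21 days of treatment. **Assumptions.** Equal arms in that trial (626/3 = 208.7), giving 1.0%, 0.5% and 9.1%. True week-8 improvement 10 points on PEA and 5 on placebo. Last observation uniform over weeks 0 to 7.

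**Planned precision.** Width = 2 × t(0.975, 50) × 15 × √(2/26) = 2 × 2.009 × 4.160 = 16.7. The half-width is 8.36; rounded to 8.4 and doubled it gives the stated 16.8. The plan's figure reproduces.

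**Bias relative to the week-8 difference.** Let k be the mean fraction of the week-8 change reached by the last observation:

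- linear course: (0+1+…+7)/64 = 0.4375
- early course, full by week 3: (0 + 1/3 + 2/3 + 5)/8 = 0.75
- late course, starting after week 4: (0.25 + 0.5 + 0.75)/8 = 0.1875

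With dropout m and true change d in the PEA (P) and placebo (C) arms, bias = −(1−k)(mP·dP − mC·dC). Positive values favour PEA.

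| Dropout PEA / placebo | mP·dP − mC·dC | Early | Linear | Late |
|---|---|---|---|---|
| 1.1% / 4.3% | 0.110 − 0.215 = −0.105 | +0.03 | +0.06 | +0.09 |
| 1.0% / 9.1% | 0.096 − 0.455 = −0.359 | +0.09 | +0.20 | +0.29 |
| 0.5% / 9.1% | 0.048 − 0.455 = −0.407 | +0.10 | +0.23 | +0.33 |
| 30% / 10% (assumed) | 3.0 − 0.5 = 2.5 | −0.63 | −1.41 | −2.03 |

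The largest value at documented rates, 0.33, is 4% of the half-width. The last row needs more dropout on PEA than on placebo, the reverse of what 1.7.4 reports.

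**Unreturned week-8 booklets, assumed 10% per arm.** Excluding those patients leaves 23.4 per arm, and the width becomes 2 × 2.014 × 15 × √(2/23.4) = 17.7, with no bias if non-return is unrelated to outcome. Carrying week 7 forward costs 0.10 × (1 − 7/8) × 5 = 0.06 points (linear) or 0.10 × 0.25 × 5 = 0.13 (late). Either choice is tolerable, but neither is specified.

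**The 10% trigger in 16.5.** It needs 8 of 78 (7.8 rounded up). With 26 patients per group, each patient's chance of a missing score is dropout + (1 − dropout) × missed-booklet rate. Binomial counts are summed over the three groups.

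| Assumed missed week-8 booklets | Expected missing | Chance of 8 or more |
|---|---|---|
| 0% | 1.7 to 2.7 | under 1% |
| 5% | 5.5 to 6.5 | 18% to 32% |
| 10% | 9.3 to 10.3 | 73% to 82% |

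The lower figures use the meta-analysis rates and the higher ones the low-back-pain trial.

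**Baseline adjustment.** If baseline and week-8 SDs both equal s, then 15² = 2s²(1−ρ), and the adjusted-to-unadjusted width ratio is √((1+ρ)/2), ignoring the small loss of degrees of freedom. The documents give no s.

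| Assumed s | ρ | Width ratio | Narrower by |
|---|---|---|---|
| 13 | 0.334 | 0.817 | 18% |
| 17 | 0.611 | 0.897 | 10% |
| 21 | 0.745 | 0.934 | 7% |

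**The case against.** The strongest reply is that the rules are open, the trial is a small estimation pilot with no primary hypothesis test, and the bias at documented dropout rates is negligible. Section 16.2.2 expects completers' booklets to be in before the analysis starts, weekly calls chase them (11.3, Appendix VIII), and weekly CIPN20 summaries by arm are planned (16.4.2.2). All of this stands and limits the severity. It does not name the target, and 16.2.2 does not cover a booklet that never arrives.

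Three stronger readings are tempting but not supported.

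- **Carry-forward seriously distorts the estimate.** A bias near 2 points appears only under assumed, strongly unequal dropout in a direction that 1.7.4 does not show.
- **The sensitivity analysis would hardly ever run.** That holds only if early stoppers are the only missing scores. An unreturned week-8 booklet is also a missing primary assessment, and at 10% non-return the trigger is more likely than not. Read literally, the 10% condition governs only the examination of mechanisms, while 16.3.1 says the sensitivity analysis will be done. How it would run below 10% is unclear, but it is not shown to be skipped.
- **A mixed model must replace carry-forward as primary.** Simulation covered 30 scenarios with both methods baseline-adjusted, an assumed baseline SD of 17 and dropout independent of outcome. Carry-forward had the lower root mean squared error in 28 of them, by 0.05 to 0.46 points. With dropout depending on the last observed change it was lower in all six scenarios. The model removes most of the week-8 bias but gives wider intervals and rests on missing at random, which cannot be checked.

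**Conclusion.** The point holds as a minor to moderate defect of definition and prespecification. The primary estimate carries an 8-week label but averages three kinds of quantity. One foreseeable kind of patient has no rule. The cited imputation is absent from 16.5, and the method-selection step there cannot be carried out as intended.

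The expected bias is +0.03 to +0.33 points against a half-width of about 8.4. This rests on dropout rates from other PEA trials, equal arm sizes in one of them, and assumed true changes and time courses. A reader might infer material bias or a need to abandon carry-forward; the figures support neither. Whether the 10% trigger is met depends on a missed-booklet rate the documents do not give. The clearest gains are a baseline-adjusted contrast, whose benefit depends on an unstated baseline SD, and a sensitivity analysis that does not depend on diagnosing the mechanism.

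**What to change.** 1. **Primary contrast (16.3.1).** Estimate each PEA versus pooled-placebo difference with adjustment for baseline CIPN20 and the stratification factors in section 5.0. The trial already collects all of these.
2. **Sensitivity analysis (16.5).** Replace the decision tree with one prespecified analysis run whatever the missing rate. For example, use a repeated-measures mixed model on all weekly CIPN20 scores giving the week-8 contrast under missing at random, plus a delta-adjusted multiple imputation. Correct the cross-reference in 16.3.1 to match.
3. **Wording, in the same edit.** Name the primary target as the last on-treatment change. State that a completer's missing week-8 score is replaced by the last available weekly score. Report results with and without the patients given an assumed zero.
4. **Consistency.** Apply the same handling to 16.4.1.2 and 16.4.2.6.

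The cost is SAP wording and modest programming, with no new patients or data. The sensitivity estimates will have somewhat wider intervals than the primary estimate. Making the mixed model primary is a legitimate option if the team wants the effect at week 8 had patients stayed on treatment, but it should be chosen for that target and not for lower total error.
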